6.3.5 Urgent safety measure

The Primary Investigator (PI) will have the authority to deviate from the protocol if doing so relates to the immediate safety of a participant, where continuing to follow protocol would put that participant at risk. This will be classed as an urgent safety measure and must be reported to the Joint research compliance office (JRCO), Medicines and Healthcare products regulatory agency (MHRA) and Research Ethics Committee (REC) within three calendar days of the occurrence. This may be reported verbally in the first instance but must be supported by a written report as soon as information is available.

6.3.6 Stopping Rules

If any of the criteria listed below are met at any time during the study, study enrolment and study therapy will be suspended pending expedited review of all pertinent data by the JRCO, MHRA and REC.

- Death in any participant, where death is attributed in any way to study therapy or intervention.
- Grade 4 anaphylaxis attributed in any way to study therapy or intervention. Grade 4 anaphylaxis per World Allergy Organization (WAO) criteria³⁵ is defined as one or more of the following:
 - Respiratory failure.
 - Life threatening hypotension or cardiovascular collapse.
 - Loss of consciousness resulting from cardiovascular collapse.

6.3.7 Premature discontinuation of study therapy

Study therapy is defined as initiation of any of the study medications described in Section 6.4 Study therapies will be discontinued for any of the following reasons:

- Two or more occurrences of grade 3 or above systemic allergic reactions after administration of study therapy. Grade 3, per World Allergy Organization (WAO) criteria, is defined as severe asthma symptoms (over 40% drop in PEF or FEV₁) *not* responding easily to an inhaled bronchodilator, and/or laryngeal oedema with stridor.³⁵
- Any adverse event (AE) and adverse reaction (AR) that, in the judgment of the principal investigator or the medical monitor, presents an unacceptable consequence or risk to the participant.
- An illness or infection that is not associated with the condition under study and that requires treatment not consistent with protocol requirements; or, if a participant develops an intercurrent illness that in the judgment of the PI in any way justifies discontinuation.
- An inability or unwillingness to comply with the study protocol, with protocol deviations sufficient to jeopardize the participant's well-being or the integrity of the study.
- Pregnancy occurring during study participation.

Participants who prematurely discontinue study treatment will be invited to complete the planned study assessments throughout the duration of the trial. However, if they decline they will undergo a follow-up visit 24 hours after discontinuation. One week after the follow-up visit, they will be contacted by telephone and discharged from the study.

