6.3.2 Inclusion Criteria

Atopic participants:

1. Adults age 18 to 65 years.
2. A clinical history of grass pollen-induced allergic rhinoconjunctivitis for at least 2 years with peak symptoms in mid-May to mid-July.
3. A clinical history of moderate to severe rhinoconjunctivitis symptoms with or without mild seasonal asthma interfering with usual daily activities or with sleep.
4. A clinical history of rhinoconjunctivitis with or without mild seasonal asthma that remains troublesome despite treatment with either antihistamines or nasal corticosteroids during the grass pollen season.
5. Positive skin prick test response, defined as wheal diameter ≥ 3 mm, to timothy grass pollen.
6. Positive specific IgE, defined as IgE immunoCAP ≥ 0.7 ISU, against timothy grass pollen.
7. For women of childbearing age, a negative urine pregnancy test at the time of screening and willingness to use an effective form of contraception for the duration of involvement in the study.
8. The ability to give informed consent and comply with study procedures.
9. A positive grass pollen nasal allergen challenge test at screening as defined by a total nasal symptom score (TNSS) of at least 7/12 after 5 minutes with an allergen dose of 5,000 BU/ml (**Appendix 6**) (see also section 6.5.7).

Healthy, non-atopic participants:

1. Adults age 18 to 65 years.
2. Negative skin prick test response to timothy grass pollen and panel of aeroallergens.
3. Negative specific IgE, defined as IgE immunoCAP < 0.35 ISU, against timothy grass pollen.
4. For women of childbearing age, a negative urine pregnancy test at the time of screening and willingness to use an effective form of contraception for the duration of involvement in the study.
5. The ability to give informed consent and comply with study procedures.

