6.3.4 Withdrawal Criteria

Participants will be advised in the Informed Consent Form that they have the right to withdraw from the study at any time without prejudice. They may also be withdrawn from the study at the investigator's discretion at any time. Reasonable effort should be made to contact any participant lost to follow-up during the course of the study in order to complete assessments. Participants who prematurely leave the study will be asked to undergo an early termination visit. The data and blood, nasal fluids, nasal brushings and nasal biopsies collected before the withdrawal will be further processed and included in analysis. Participants who prematurely leave the study will not be replaced.

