6.4 Study medications

6.4.1 Allergen Immunotherapy Tablet (AIT)

Grazax® is a fast-dissolving tablet that is registered throughout Europe for sublingual use in patients aged 5–65 years (18–65 years in UK)^{14, 15, 16}. The tablet is administered daily for a minimum of 2 months before and during the grass pollen season. In a double-blind trial of Grazax® that included a withdrawal phase, efficacy was maintained for 2–3 years with continuous treatment^{15, 16} and at 1 year following withdrawal^{17, 18}. AIT

has been shown to be safer than the injection route. It is recommended that the first dose of Grazax® is administered in the clinic and that subsequent doses are taken independently by the patient. Local side effects of itching and swelling in the mouth are common, occurring in 50% to 60% of individuals within minutes and resolving within 1 hour with a median half-life of approximately 10 days with daily administration^{14, 15, 16}. These responses are, in general, well tolerated and require no treatment. In a recent large trial involving over 600 patients, the withdrawal rate was 5% as compared to 3% in placebo-treated patients^{14, 15}. More severe local and systemic reactions have been reported, but they are excessively rare and no fatalities have occurred¹⁹.

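### Section 6.3.7 stops the tablet for pregnancy and for repeated grade 3 or above systemic reactions, but still invites these participants to grass allergen provocation and nasal biopsy

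*Protocol*

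**What the plan says.** Protocol section 6.3.7 lists five reasons for stopping study therapy. Two matter here: "Two or more occurrences of grade 3 or above systemic allergic reactions after administration of study therapy" and "Pregnancy occurring during study participation". Grade 3 is described there as severe asthma symptoms with a fall of over 40% in PEF or FEV1 that does not respond easily to a bronchodilator, and/or laryngeal oedema with stridor.

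The closing paragraph of the section treats all five reasons alike: "Participants who prematurely discontinue study treatment will be invited to complete the planned study assessments throughout the duration of the trial". The only other path is for a participant who declines, who has a visit 24 hours after discontinuation and a telephone call a week later. The ITT definitions (protocol 6.8.2, SAP section 3) repeat the invitation for participants who drop out, also without exception.

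Section 6.5.14 sets what is planned in the blinded year. Visit 5 has a nasal biopsy. Visit 6 has a nasal grass challenge. Visit 7 repeats Visit 0b: nasal challenge, duplicate intradermal grass allergen and biopsy. SAP section 7.3.2 lists no biopsy at the Visit 5 time point.

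**The concern.** The tablet and the challenge extract come from the same source, timothy grass (6.4.2 and 6.5.7). A participant whose tablet was stopped for repeated severe systemic reactions is therefore still offered that allergen by two other routes. A participant whose tablet was stopped for pregnancy is still offered allergen provocation, and a biopsy that uses cocaine, phenylephrine and adrenaline (6.5.11). These procedures serve the research only, and 6.3.7 itself foresees both situations.

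The entry criteria show that the protocol already treats such conditions as relevant to the procedures. Non-atopic controls never take the tablet. Yet they need a negative pregnancy test and "willingness to use an effective form of contraception for the duration of involvement in the study", and a history of life-threatening anaphylaxis or angioedema excludes them (6.3.2, 6.3.3). Tablet exposure cannot explain those criteria. There is no matching rule for atopic participants when the condition arises during the trial. The parallel is not exact for reactions, since grade 3 is not the same as life-threatening anaphylaxis, but it is direct for pregnancy.

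**Working it through.** **1. Is there an exception elsewhere?** Sections that could contain one:

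- 6.3.4: discretionary withdrawal from the whole study; not tied to a reason or a procedure.
- 6.3.5: authority to deviate for immediate safety; reportable to the JRCO, MHRA and REC within three calendar days.
- 6.3.6: a death or grade 4 anaphylaxis attributed to therapy or intervention suspends enrolment and therapy; the procedures are not named.
- 6.4.4: after a severe systemic reaction, only the tablet is withheld.
- 6.7.6.6: counselling, monitoring and reporting of pregnancy; no mention of the procedures.
- Section 7: allows alternative treatment and keeps the participant in follow-up.
- 6.8.2 and SAP section 3: repeat the invitation.

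None requires challenge, intradermal allergen or biopsy to be omitted.

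**2. Largest exposure offered in the blinded year**, if the participant accepts everything and no clinician intervenes. One challenge is 5,000 BU/ml × 0.1 ml × 2 nostrils = 1,000 BU. A biopsy session is three bites.

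| Tablet stopped | Nasal challenges | Intradermal injections (1 BU each) | Biopsy sessions |
|---|---|---|---|
| Before Visit 5 | 2 (2,000 BU) | 2 | 2 (1 under the SAP) |
| Between Visits 5 and 6 | 2 (2,000 BU) | 2 | 1 |
| Between Visits 6 and 7 | 1 (1,000 BU) | 2 | 1 |

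**3. How many people?** The documents give no rate for these two reasons. Section 6.4.1 reports from an earlier large trial that "the withdrawal rate was 5% as compared to 3% in placebo-treated patients". Assuming those rates carry over:

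- 44 randomised: 22 × 0.05 + 22 × 0.03 = 1.76
- 50 randomised: 25 × 0.05 + 25 × 0.03 = 2.0

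These are withdrawals for any reason, so they are a ceiling under that assumption. The expected number for the two reasons is smaller and may be zero.

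**4. What would withholding cost in power?** Inputs from 6.8.1: mean 4.63, SD 1.65, 30% reduction, two-sided 0.05. The standardised difference is d = 0.30 × 4.63 / 1.65 = 0.842.

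The plan states 80% at 22 per group. By the normal approximation, 0.842 × √(22/2) = 2.792 and Φ(2.792 − 1.960) = 79.7%, which reproduces it. The exact two-sample t-test (noncentrality 2.792, 42 df) gives 77.9%, used here as the reference.

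- One value lost per arm (21 v 21): 75.9%
- Two lost from one arm (22 v 20): 75.8%

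**5. Could the loss bias the result?** Possibly, if it falls more on active. As illustration only, suppose each lost active value would have equalled the placebo mean. The full active mean is 0.70 × 4.63 = 3.241 and the effect is 4.63 − 3.241 = 1.389.

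- One lost: (22 × 3.241 − 4.63)/21 = 3.175, overstating the effect by 0.066 (4.8%)
- Two lost: (22 × 3.241 − 9.26)/20 = 3.102, overstating it by 0.139 (10.0%)

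**The case against.** The strongest reply is that an invitation does not displace clinical judgement. The participant may decline. The investigator may act under 6.3.4 ("They may also be withdrawn from the study") without the three-day report attached to 6.3.5, and 6.3.5 itself covers cases "where continuing to follow protocol would put that participant at risk". A physician and anaphylaxis treatment are always present at skin tests (6.5.9). A grade 4 reaction attributed to therapy or a procedure already triggers expedited review. Every treated participant was scheduled for these procedures before the first tablet: nasal challenge at screening and Visit 0b, intradermal allergen and biopsy at Visit 0b. Severe reactions to the tablet are also described as uncommon: "they are excessively rare and no fatalities have occurred".

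All of this stands as a reason to expect little harm. It does not supply the missing rule. Withdrawal under 6.3.4 is blunt, because it also gives up harmless questionnaire and safety data. Section 6.3.5 is meant for immediate danger and fits poorly with a pregnancy known months before a visit. The reassurance on intradermal testing (6.5.9, 6.7.1.2) concerns grass-allergic people generally, and having tolerated the procedures at baseline says little about someone who has since had two grade 3 reactions.

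A reader might infer that the same default should follow any adverse event judged an unacceptable risk. The documents do not support that. Such an event could be a local mouth reaction: 6.4.1 puts local itching and swelling at 50% to 60%, and Table 6 defines local grade 3 partly by discontinuation. It need not bear on skin testing or biopsy, and the investigator or medical monitor has already judged the individual case.

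The power figures assume a two-group comparison at 12 months, as in 6.8.3.1. SAP section 7.2.1 describes longitudinal modelling over baseline, 6 and 12 months, so the loss may differ.

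**Conclusion.** The gap is real and worth closing, but narrow. For pregnancy and for two or more grade 3 or above systemic reactions, the plan as written offers avoidable, research-only risk, and no provision requires the procedures to be left out.

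It would be too strong to say that the protocol compels anyone to undergo them, or that several participants will be exposed. Attendance is voluntary, and the figure of 1.8 to 2.0 covers withdrawal for every reason, carried over from another trial. Harm also requires the participant to accept and no clinician to step in. The case rests on how serious and how avoidable the risk is, not on its frequency.

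Nor does the point call for an analysis that sets missing active values to the placebo mean. That is one arbitrary value, used above only to show scale.

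One limit: the consent pages, the cited safety procedure and the product information are not available here and may contain relevant guidance.

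**What to change.** Amend the last paragraph of 6.3.7:

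- **Tablet stopped for pregnancy:** withhold nasal allergen challenge, intradermal allergen and nasal biopsy.
- **Tablet stopped for two or more grade 3 or above systemic reactions:** withhold nasal challenge and intradermal allergen in both arms, so that the rule does not depend on unblinding. Biopsy gives no allergen and can be left to documented investigator judgement.
- **In both cases:** continue questionnaires, symptom and medication scores and safety follow-up. Take blood, nasal fluid and brushing samples if judged safe.

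Add a cross-reference in protocol 6.8.2 and SAP section 3: the participant stays in the ITT set, and withheld values are recorded as missing with the reason.

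The text change is small. The statistical price is the occasional missing Visit 7 primary value, possibly more often on active, amounting to about two percentage points of power if two values are lost.

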6.3.8 Randomisation

After the screening phase eligible participants will be randomised, double-blind, to one of the two treatment arms in a 1:1 ratio and assigned a randomisation ID number. Additionally, the participant will be assigned a specific investigational medical product (IMP) kit, from those available at the site that corresponds to the treatment assignment. Each participant will be assigned a kit ID from the site's inventory whose treatment

matches the group to which the participant was randomized. The treatment assignment notification will be sent to authorized study personnel and the investigational pharmacy via email and/or fax. (The healthy, non-atopic control group will not be randomized to a treatment arm but investigators analysing biological samples from these participants will be blinded as to their origin.)

6.3.9 Blinding

Blinding will be maintained for all study participants throughout the first 12 months of the study. Data analysis for primary and secondary endpoints will be performed after 1 year (efficacy endpoints).

6.3.10 Unblinding

Unblinding before the first 12 months of the study is completed will occur only if a participant's well-being is threatened and the investigator believes unblinding is necessary to protect the participant. In this event, 24-hour access for emergency unblinding will be provided. Unblinding will be provided by on-site Pharmacy 24 hours a day/7 days a week after authorisation by the Principal Investigator. A full account of the event will be recorded, including the date and time of the emergency, the reason for the decision to unblind, and the names of the medical monitor and others who were notified of the emergency. During site visits, the site monitor must verify that the protocol chair was notified and that a written account was completed. The reasons for unblinding of a participant's treatment will be included in the final study report (see also section 6.7.6.5).

6.4 Study medications

6.4.1 Allergen Immunotherapy Tablet (AIT)

Grazax® is a fast-dissolving tablet that is registered throughout Europe for sublingual use in patients aged 5–65 years (18–65 years in UK)^{14, 15, 16}. The tablet is administered daily for a minimum of 2 months before and during the grass pollen season. In a double-blind trial of Grazax® that included a withdrawal phase, efficacy was maintained for 2–3 years with continuous treatment^{15, 16} and at 1 year following withdrawal^{17, 18}. AIT

has been shown to be safer than the injection route. It is recommended that the first dose of Grazax® is administered in the clinic and that subsequent doses are taken independently by the patient. Local side effects of itching and swelling in the mouth are common, occurring in 50% to 60% of individuals within minutes and resolving within 1 hour with a median half-life of approximately 10 days with daily administration^{14, 15, 16}. These responses are, in general, well tolerated and require no treatment. In a recent large trial involving over 600 patients, the withdrawal rate was 5% as compared to 3% in placebo-treated patients^{14, 15}. More severe local and systemic reactions have been reported, but they are excessively rare and no fatalities have occurred¹⁹.

6.4.2 Formulation and Packaging

GRAZAX® and GRAZAX® PLACEBO SQ Standardized Grass Allergy Immunotherapy (Grazax®, ALK- Abello Horsholm, Denmark) is formulated as a freeze-dried oral lyophilisate/orally disintegrating tablet for oromucosal use. The active pharmaceutical ingredient is a standardized allergen extract derived from extraction and purification of grass pollen from timothy grass (*Phleum pratense*). The biological activity of the allergen is expressed in standardized quality units (SQ). The recommended dosage is one oral lyophilisate containing 75,000 SQ Tablet units (SQ-T) or approximately 2800 Bioequivalent allergy units (BAU), a measure of *Phleum pratense* SQ total biological potency defined by the Food and Drug Administration (FDA). This dose is equivalent to 15 µg of *Phleum pratense* major allergen. The non-active ingredients consist of fish gelatin, mannitol, sodium hydroxide and water. Grazax® placebo is a tablet whose composition is identical to the active Grazax® tablet with the only exception being exclusion of the active pharmaceutical ingredient, *Phleum pratense* SQ. Grazax® and Grazax® placebo tablets will be supplied in blister packs by ALK-Abello. For the participants the study medication will be free of charge.

6.4.3 Administration

The first Grazax® or Grazax® placebo will be administered under the supervision of the trial physician and the participant observed for one hour thereafter before discharge from the clinic. This will take place on Visit 1, which will be conducted 1 day after the

second baseline visit (V0b). Thereafter, home sublingual administration of Grazax® or Grazax® placebo tablets will occur daily during the 12 months of the trial. In those participants who received active treatment a continuation of daily treatment will take place for another 12 months. Those participants who received placebo will be offered 24 months of active treatment after completion of the first 12 months and after unblinding. Tablets should be removed from the blister packs with dry fingers and should be taken immediately after opening the blister. Each tablet should be placed underneath the tongue until fully dissolved (1–2 minutes). Swallowing should be avoided for about 1 minute. Food and beverage should not be consumed for the following 5 minutes. For additional information on the preparation and administration of Grazax®, please refer to the following uniform resource locator (URL):

http://www.grazax.com/SiteCollectionDocuments/Grazax.com/About%20Grazax/Grazax_SmPC_MRP_VAR13_15OCT2010.pdf

6.4.4 Special Warnings and Precautions for Use

In case of oral surgery, including dental extraction, treatment with Grazax® should be stopped for 7 days to allow healing of the oral cavity. Mild to moderate local allergic reactions such as itching or swelling of the mouth may occur during treatment. If significant local adverse reactions occur treatment with antihistamines should be considered. Rare cases of severe systemic allergic reactions have been reported with Grazax® use. Therefore medical supervision at the start of treatment is an important precaution. All participants will be provided with an emergency telephone contact number for study personnel with 24 hour availability. The onset of systemic symptoms may include flushing, itching in the extremities and other areas of the body, general discomfort and agitation. In cases of severe systemic reactions including angioedema, difficulty swallowing or breathing, throat fullness or hypotension, Grazax® should be discontinued and a physician contacted immediately. Severe systemic reactions may be treated with adrenaline. Treatment with Grazax® should remain withheld until evaluation by a study physician. If participants with concomitant asthma experience symptoms and signs indicating asthma deterioration, treatment should be discontinued and a study physician consulted immediately. Grazax® contains fish-derived gelatin. The available data have not indicated an increased risk of allergic reactions in severe

fish allergic patients. However as a precaution, patients will be asked during screening whether they are allergic to vertebrate/finned fish. If the history is positive, a skin test and/or specific IgE test to vertebrate/finned fish will be requested and if positive the subject will not be included in the study.

6.4.5 Recommended Storage Conditions

Grazax® tablets are sensitive to moisture and blister packs should be stored unopened until use. The current formulation has been shown to be stable when stored at room temperature in unopened blisters.

6.4.6 Drug accountability

The investigator is required to maintain adequate records of the disposition of the investigational product, including the date and quantity of drug that was received, the participants to whom drug was dispensed (participant by participant accounting), and an account of any drug accidentally or deliberately destroyed. Records for receipt, storage, use, and disposition of the study drug will be maintained by the study site. A drug-dispensing log will be kept current for each participant and will contain the identification of each participant and the date and quantity of drug dispensed. All records regarding disposition of the investigational product will be available for inspection by the clinical trial monitor.

